7.2.1.3 Subgroup Analyses of Primary Endpoint

The primary efficacy analysis will be performed for the following subgroups for the PP population:

- Sex (male and female);
- Age (< 50 and \geq 50 years);
- Race (white and not white);
- Hypertensive status (no medical diagnosis of or treatment for hypertension; medical diagnosis of hypertension treated with 0-2 antihypertensive agents; or medical diagnosis of hypertension treated with 3 or more antihypertensive agents).

The primary efficacy analysis for the subgroup medical diagnosis (T2DM and obstructive sleep apnea) may be performed if applicable.

7.2.2 Analyses of Secondary Endpoints

Secondary endpoints including change from baseline to Week 8 in mean DBP as measured by 24-hr ABPM, mean change in SBP and DBP from baseline to Week 8 as measured in clinic will be analyzed for the PP population using a similar ANCOVA model structure as that of the primary analysis. The model will comprise of treatment, stratification factors (sex, age and hypertensive status) and baseline value of the dependent variable as a covariate. Adjusted means (LS Mean \pm standard error) with associated two-sided 95% confidence intervals for the between-treatment comparisons and for the changes from baseline will be reported.

The estimand, estimator, and estimate of these secondary endpoints are defined as follows:

Estimand	Population	Per Protocol
Endpoint		Changes from Baseline in Variable X at Week 8

	How to account for intercurrent events	The treatment policy strategy will be followed, whereby the observed value (if not missing) for the endpoint of interest will be used for analysis.
	Population-level summary	The between-treatment difference in changes from baseline to Week 8 in Variable X.
Estimator	Analysis	ANCOVA with treatment, stratification factors (sex, age and hypertensive status) and baseline value of variable X as a covariate.
Estimates	Primary to support the estimand	Between-group comparison (effect in VI-0521 minus effect in placebo [or phentermine]): 
 ✓ LSM for the between-group difference ✓ 95% CI of the LSM ✓ p-value
Estimates	Tributary	Within-treatment group comparison (effect at Week 8 minus the value at baseline): 
 ✓ LSM for the within-group difference ✓ 95% CI of the LSM ✓ p-value

Similar imputation method as described in [Section 7.2.1](#) will be carried out for missing DBP values from the 24-hr ABPM. For missing clinic SBP and DBP, data will not be imputed after mapping unscheduled visits.

Additionally, supportive analysis of the 24-hr mean DBP endpoint will be carried out similarly as described in [Section 7.2.1.2](#). Supportive analysis of the clinical SBP and DBP endpoint will be performed using the observed case data for the ITT population. Extra sensitivity analyses similar to the primary endpoint may be conducted on the secondary endpoints if applicable.

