11.3 Vital Signs

Vital signs (systolic blood pressure, diastolic blood pressure, heart rate, respiration rate, temperature) will be assessed at Screening, Randomization, Week 4, and Week 8/end of study or early termination. Subjects should be seated comfortably for at least 10 minutes prior to assessing vital signs. Heart rate and respiratory rate measurements should be made by counting events (heartbeats or breaths) for a period of 30 seconds and multiplying these values by 2 to obtain the rates per minute. A calibrated blood pressure monitor should be employed for blood pressure measurements. The same cuff should be used for the same subject across multiple visits when blood pressure is performed. The same person should perform all assessments for a given subject.

Clinic blood pressure for determining hypertension should be the average of three successive BP readings, collected at least 2 minutes apart. The mean of the three values will be recorded as the subject's blood pressure.

11.4 24-hr Ambulatory Blood Pressure Monitoring (24-hr ABPM)

At Baseline and at Week 8/end of study or early termination, 24-hr ABPM will be performed non-invasively using a validated oscillometric monitor provided by a central vendor. Blood pressure and heart rate will be measured every 20 minutes from 6:00 to 22:00 hours, and every 30 minutes from 22:01 to 5:59 hours for 24 consecutive hours, while subjects continue normal routine activities. The monitor will be attached in the morning and removed after at least 24 hours. Data will be uploaded to a computer at the end of the recording session and prior to discharging the subject from the study visit, site staff will review the data to assure that: (1) at least 80% of the readings are valid, (2) there are at least 24 hours of data, and (3) there are no more than two consecutive hours of missing data. If any of these criteria are not satisfied, subjects will be asked to repeat the assessment for an additional 24 hours. ABPM hook up will be done by qualified staff.

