13.2 Sample Size Determination

Approximately 555 subjects (185 per group) will be randomized to top-dose VI-0521, phentermine 30 mg, or placebo. Assuming a standard deviation of 10 mmHg for change in mean

24-hr SBP as measured by ABPM, the intended sample size of 185 subjects per treatment group will provide 80% power to detect superiority of VI-0521 to comparator treatments (placebo or phentermine) if the comparator subtracted change in mean SBP has a value of less than -3.0 mmHg, and will provide 80% power to demonstrate non-inferiority based on a non-inferiority margin of 3 mmHg if the comparator subtracted change in mean SBP is less than 0.0 mmHg. The above-mentioned calculations were based on two-sample equal variance t-test at 2-sided alpha=0.05 for demonstrating superiority and at 1-sided alpha=0.025 for demonstrating non-inferiority. This sample size estimate also accounts for a 5% drop-out rate over the course of the study.

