7.1.3 Baseline and Change from Baseline

In general, the baseline value for each variable is defined as the last non-missing observation obtained prior to the dispense of the first study drug. The actual first randomized dose date/time will be compared to the date/time of data collection to define the baseline for each parameter. In the case where the last non-missing measurement (except AE and concomitant medications) and the first dose coincide at the same time, or the same date if time of the measurement is not collected, that measurement will be considered as baseline value. The change from baseline value is defined as post-baseline value minus baseline value. The percent change from baseline value is defined as $(\text{post-baseline value} - \text{baseline value}) / \text{baseline value} \times 100$.

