8 POWER AND SAMPLE SIZE

Approximately 555 subjects (185 per group) will be randomized to top-dose VI-0521, phentermine 30 mg, or placebo. Assuming a standard deviation of 10 mmHg for change in 24-hr mean SBP as measured by ABPM, the intended sample size of 185 subjects per treatment group will provide 80% power to detect superiority of VI-0521 to comparator treatments (placebo or phentermine) if the comparator subtracted change in mean SBP has a value of less than -3.0 mmHg, and will provide 80% power to demonstrate non-inferiority based on a non-inferiority margin of 3 mmHg if the comparator subtracted change in mean SBP is less than 0.0 mmHg. The above-mentioned calculations were based on two-sample equal variance t-test at 2-sided $\alpha=0.05$ for demonstrating superiority and at 1-sided $\alpha=0.025$ for demonstrating non-inferiority. This sample size estimate also accounts for a 5% drop-out rate over the course of the study.

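### The clinic SBP and DBP models leave two pre-randomisation blood pressure measures unused: a modest loss of precision that depends on assumed correlations, not a bias

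*SAP*

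**What the plan says.** SAP 7.2.2 sets the model for 24-hr DBP and for clinic SBP and DBP in one sentence: "The model will comprise of treatment, stratification factors (sex, age and hypertensive status) and baseline value of the dependent variable as a covariate". The estimator row of the table in that section repeats it. SAP 7.1.3 adds that "the baseline value for each variable is defined as the last non-missing observation obtained prior to the dispense of the first study drug". For clinic BP this is the Visit 2A value, and the screening value is only a fallback.

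Protocol 11.3 describes the measurement: "Clinic blood pressure for determining hypertension should be the average of three successive BP readings, collected at least 2 minutes apart". The schedule of events applies the same three-reading average at Visits 2A and 4A.

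Two other blood pressure measures precede randomisation:

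- **Screening clinic BP.** It is scheduled for every subject and needed for exclusion 1 in Protocol 8.2.
- **Baseline 24-hr ABPM.** It starts at Visit 2A and must be verified before the randomisation call at Visit 2B (Protocol 10.2).

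SAP 7.2.2 analyses the clinic endpoints in the PP population. SAP 5.4 admits a subject to that population only with at least 23.5 hours of baseline ABPM and at least 75% of readings present. In SAP 7.1.2.1, clinic SBP and DBP come last in the hierarchy, after all tests on 24-hr SBP and 24-hr DBP.

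**The concern.** Averaging three readings a few minutes apart reduces within-visit noise but leaves visit-to-visit variation untouched. One visit is therefore an imperfect measure of a subject's usual clinic BP. A second clinic visit and a 24-hr mean should each carry further information about Week 8 clinic BP, and both are already in the database at no extra cost.

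Prespecified covariates measured before randomisation narrow the interval for the treatment difference without changing what it estimates. Clinic SBP and DBP belong to the family protected for type I error, no power is stated for them, and missing clinic values are not imputed. Precision on these endpoints is worth having if it costs almost nothing.

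**Working it through.** **The plan's own figure.** The SAP's only variance and power statement concerns 24-hr SBP: "Assuming a standard deviation of 10 mmHg for change in 24-hr mean SBP as measured by ABPM", and "the intended sample size of 185 subjects per treatment group will provide 80% power to detect superiority of VI-0521" at a difference of 3 mmHg. Per group, n = 2 × 10² × (1.960 + 0.842)² / 3² = 174.4, so 175. With 5% dropout, 175 / 0.95 = 184.2, so 185. It reproduces, but it says nothing about clinic BP.

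**Assumed inputs (none is in the documents).**

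- r: correlation between Visit 2A and Week 8 clinic SBP, and between screening and Visit 2A; 0.5, 0.6 or 0.7, taken as conditional on the stratification factors.
- s: correlation between screening and Week 8; equal to r, or lower by 0.10 or 0.15. Screening may be up to 4 weeks before baseline, so about 12 weeks before Week 8.
- q: correlation of the baseline 24-hr mean with usual clinic BP, 0.5 to 0.8; its correlation with any single clinic visit is then q√r.
- Screening SBP: mean 128, SD 13 mmHg before the eligibility cut at 140.

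Because Visit 2A is a covariate, the residual variance is the same for change as for the Week 8 value.

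**Without the eligibility cut.** Adding screening BP to Visit 2A removes the fraction [(s − r²)/(1 − r²)]² of residual variance. At r = 0.6:

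- s = 0.6: (0.24/0.64)² = 14.1%
- s = 0.5: (0.14/0.64)² = 4.8%
- s = 0.45: (0.09/0.64)² = 2.0%

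**With the cut.** Put b = (140 − 128)/13 = 0.923 and λ = φ(b)/Φ(b) = 0.317. Screening variance shrinks to 1 − bλ − λ² = 0.607 of its uncut value. Every other covariance loses (1 − 0.607) times the product of the two correlations with screening.

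Example, r = s = 0.6:

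- Variance at Visit 2A and at Week 8: 1 − 0.36 × 0.393 = 0.8585.
- Their covariance: 0.6 − 0.36 × 0.393 = 0.4585.
- Residual variance on Visit 2A alone: 0.8585 − 0.4585²/0.8585 = 0.6136.
- Residual variance with screening added: 1 − 2 × 0.36/1.6 = 0.55, which selection on screening does not change.
- Reduction: 1 − 0.55/0.6136 = 10.4%.

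The same steps, with the 24-hr mean as a third covariate, give these reductions in residual variance for SBP:

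| r | s | Screening only | Both, q = 0.5 | Both, q = 0.8 |
|---|---|---|---|---|
| 0.5 | 0.50 | 7.8% | 10.1% | 16.3% |
| 0.5 | 0.40 | 2.7% | 6.0% | 14.8% |
| 0.5 | 0.35 | 1.2% | 5.0% | 15.3% |
| 0.6 | 0.60 | 10.4% | 12.2% | 17.9% |
| 0.6 | 0.50 | 3.4% | 6.3% | 14.9% |
| 0.6 | 0.45 | 1.4% | 4.8% | 15.1% |
| 0.7 | 0.70 | 13.3% | 14.7% | 19.3% |
| 0.7 | 0.60 | 3.5% | 6.0% | 13.9% |
| 0.7 | 0.55 | 1.0% | 4.1% | 14.1% |

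Screening alone thus gives about 1-13%, and both covariates about 4-19%. In interval width, √(1 − 0.04) = 0.980 and √(1 − 0.19) = 0.900, so 2-10% shorter.

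**Outside this grid.** An assumed screening mean of 120 raises the top of the range for both covariates to 21.1%. Steeper decay lowers the bottom: with r = 0.7, s = 0.49 and a 24-hr mean correlated 0.5 with the two pre-treatment clinic values but 0.4 with Week 8 (no cut), both covariates together give 0.7%.

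**The case against.** The strongest reply is that nothing here is wrong. ANCOVA on the baseline value and the stratification factors is prespecified and unbiased, and it follows Protocol 13.1.3, which applies the primary method to the secondary endpoints. This stands: a richer covariate set is an improvement, not a correction.

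A reader might infer a firm loss, of the order of 8-18% of residual variance. The documents do not support one, since they hold no clinic SD, no visit-to-visit correlation and no ABPM-to-clinic correlation. Figures of that size come mainly from assuming that screening predicts Week 8 as well as Visit 2A does. A drop of 0.10 in that one correlation cuts the screening-only gain to about 3-4%. The upper ABPM assumption is also generous: q = 0.8 implies single-visit correlations of 0.57 and 0.62 at r = 0.5 and 0.6, so the 24-hr mean would predict Week 8 clinic BP better than clinic BP itself does.

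A reader might also infer a gain in power for the clinic claims. That cannot be computed. The 3 mmHg effect and the 5% dropout belong to the 24-hr SBP calculation, and the PP sample size is unknown. The clinic tests are reached only if all four primary tests and all four 24-hr DBP tests succeed, so stand-alone power is not the chance of a confirmatory clinic result.

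Finally, extra covariates bring a missing-value question in the supportive ITT analysis. SAP 7.2.1.1 expects some ITT subjects to lack more than 25% of baseline readings. That is a fair point and needs a rule.

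**Conclusion.** The point holds as a modest, inexpensive gain in precision. Two prognostic measures taken before randomisation go unused in the clinic SBP and DBP models. For SBP, under the assumed correlations, using both would cut residual variance by roughly 4-19%, with smaller gains if correlations decay faster than assumed. No figure is offered for DBP. There is no bias and no type I error inflation, and the primary analysis and the sample size of 185 per group are untouched. The benefit reaches only the last endpoints in the hierarchy, so this is worth doing but low in priority.

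**What to change.** Before unblinding, amend SAP 7.2.2 for the two clinic endpoints only. In the model sentence and the estimator row, add two continuous covariates: screening clinic SBP (DBP for the DBP model) and baseline 24-hr mean SBP (DBP). Keep change from Visit 2A as the response, and leave the testing order as it is.

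Every PP subject has baseline ABPM by definition, so the clinic PP analysis loses no one on that account. For the supportive ITT observed-case analysis, state one rule in advance: either take the baseline 24-hr mean from whatever readings exist, or keep the planned covariate set there.

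The cost is two degrees of freedom, a few lines of SAP text, and a clinic model that differs slightly from the primary model. No new data, visits or subjects are needed.

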7.2.3 Analysis of Exploratory Endpoints

Analysis of exploratory endpoints will be performed on the PP population using the observed case data.

All change from baseline exploratory endpoints will be analyzed using ANCOVA models in a similar manner to the primary and secondary endpoints. For the endpoints on percentage of subjects with a normal SBP and DBP ‘dipping pattern’ at Week 8, a Cochran-Mantel-Haenszel (CMH) χ^2 test that is stratified by sex, age and hypertensive status will be used for analysis. Corresponding estimates of the common Mantel-Haenszel relative risk will be provided along with 95% confidence intervals (CIs). For the endpoints on percentage of subjects meeting the BP or heart rate thresholds, descriptive summary will be provided.

Example SAS codes for CMH test are:

No sensitivity analysis is planned for the exploratory endpoints.

In addition, all 24-hr ABPM measurements including blood pressure and heart rate that are summarized in the endpoints will be presented in a listing.

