9.4.3 Administration

Investigators will instruct subjects to take 1 capsule of study drug every morning with or without food. Capsules must be taken whole, and should not be broken or split apart in any manner. When dispensing titration blister cards, investigators should ensure that subjects understand that each blister card contains a 4-week supply of study drug, and that the capsules must be taken in a specific order (i.e., Week 1 before Week 2, and Week 3 before Week 4).

When dispensing study drug bottles, investigators should ensure that subjects understand that each bottle contains a 4-week supply of study drug and that each bottle contains extra capsules that should only be taken for special circumstances (e.g. capsule is accidentally dropped and cannot be retrieved or subject cannot return to the end of study visit within window). Study drug will not be dispensed until the morning of Day 2 after the ABPM device is removed following the baseline 24-hr recording and data has been confirmed to be compliant.

Subjects will be instructed to withhold dosing of study drug on study visit days until after certain procedures are completed.

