10.2 Baseline/Randomization (Visit 2, Week 0/Beginning of Titration)

The following activities will take place at Visit 2A (first day of 2-day visit):

- Assess inclusion/exclusion criteria (applicable criteria referencing the baseline visit);
- Obtain body weight;
- Obtain vital signs (blood pressure, heart rate, respiration rate and temperature);
- Record any adverse events reported or observed;
- Record any changes in concomitant medications;
- Perform a urine pregnancy test (WOCBP only) and remind subject about contraception. If the subject is pregnant, she will not qualify for the study;
- Set up 24-hr ABPM monitoring equipment, and initiate monitoring;
- Provide subject with instructions for proper handling of ABPM device and remind the subject to return to the clinic in 24 hours to complete evaluation.

The following activities will take place at Visit 2B (second day of 2-day visit):

- Record any adverse events reported or observed;
- Record any changes in concomitant medications;

- End 24-hr ABPM monitoring, disconnect devices, and upload data;
- Contact EDC/RTSM to obtain randomization assignment for subject upon verifying successful ABPM; if verification of successful ABPM cannot be made, repeat 24-hr ABPM setup as described for Visit 2A and bring subject back in 24 hours to complete evaluation;
- Dispense study drug and instruct the subject to take one capsule every morning (with or without food) in the order indicated on the blister card ([Section 9.4.3](#)) and advise on lifestyle counseling. Subject should also be instructed to withhold dosing on the morning of the next scheduled study visit; and
- Schedule the next study visit in 4 weeks (28 ± 3 days).

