4.3 Exploratory Endpoints

The exploratory endpoints of the study are:

- Mean hourly changes in SBP and DBP from baseline to Week 8, defined as the mean change from baseline at each hour;
- Change in mean daytime and nighttime SBP as measured by 24-hr ABPM from baseline to Week 8;

- Change from baseline to Week 8 in nighttime “dipping” of SBP, and the percentage of subjects with a normal SBP “dipping” pattern at Week 8. A normal “dipping” pattern of SBP will be defined as a reduction of mean nighttime SBP of $\geq 10\%$ relative to mean daytime SBP during the same 24-hr recording;
 - SBP dipping is calculated as: $100 \times [(\text{mean daytime SBP} - \text{mean nighttime SBP}) / \text{mean daytime SBP}]$
- Change from baseline to Week 8 in nighttime “dipping” of DBP, and the percentage of subjects with a normal DBP “dipping” pattern at Week 8. A normal “dipping” pattern of DBP will be defined as a reduction of mean nighttime DBP of $\geq 10\%$ relative to mean daytime SBP during the same 24-hr recording;
 - DBP dipping is calculated as: $100 \times [(\text{mean daytime DBP} - \text{mean nighttime DBP}) / \text{mean daytime DBP}]$
- Percentage of subjects meeting the following BP thresholds at baseline and Week 8 as measured by 24-hr ABPM;
 - SBP: ≥ 160 mmHg for 2 consecutive readings; ≥ 180 mmHg for 2 consecutive readings;
 - DBP: ≥ 100 mmHg for 2 consecutive readings; ≥ 110 mmHg for 2 consecutive readings;
- Percentage of subjects with the average of three successive BP meeting the following thresholds at baseline and each post-baseline visit as measured in clinic;
 - SBP: ≥ 160 mmHg; ≥ 180 mmHg; ≥ 20 mmHg increase from baseline;
 - DBP: ≥ 100 mmHg; ≥ 110 mmHg; ≥ 15 mmHg increase from baseline;
- Change from baseline to Week 8 in mean 24-hr heart rate, mean daytime heart rate, mean nighttime heart rate, and mean hourly heart rate;
- Percentage of subjects meeting the following heart rate thresholds at baseline and Week 8 as measured by 24-hr ABPM;
 - > 100 bpm for 2 consecutive readings; > 100 bpm for at least 1 hour; > 100 bpm for at least 2 hours; > 100 bpm for at least 3 hours; > 100 bpm for at least 4 hours; mean daytime heart rate > 100 bpm;
- Percentage of subjects meeting the following heart rate thresholds at baseline and each post-baseline visit as measured in clinic;
 - > 100 bpm;
 - ≥ 10 bpm increase from baseline; ≥ 20 bpm increase from baseline

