5.4 Per Protocol (PP) Population

PP Population will be comprised of ITT subjects who met all of the following criteria:

- Compliant to study treatment (defined as $\geq 80\%$ treatment compliance as specified in [Section 6.5](#));
- Last daily dose of study drug administered on the same date that ABPM was initiated at Visit 4A (first day of Week 8/End of Study or Early Termination);
- Had at least 23.5 hours of ABPM data (i.e. blood pressure and heart rate data) at baseline and at Week 8/End of Study or Early Termination, and at least 75% of 24-hr ABPM readings (or equivalently 48 readings during the 24-hr period) are not missing;
- Subjects with any major protocol deviation that had impact on ABPM readings will be excluded from the PP Population.

The PP population will be used to assess the primary and secondary endpoints as primary analyses. Subject inclusion in the PP population will be determined and documented prior to database lock and treatment unblinding.

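### Heart-rate threshold counts and ambulatory heart rate are reported on per-protocol observed cases only, so some treated subjects are left out even of the Week 4 clinic counts

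*SAP*

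**What the plan says.** SAP 4.3 lists three groups of heart-rate endpoints as exploratory: changes in 24-hour, daytime, nighttime and hourly ambulatory means; ambulatory counts above 100 bpm; and a clinic set described as "Percentage of subjects meeting the following heart rate thresholds at baseline and each post-baseline visit as measured in clinic". Each post-baseline visit includes Week 4. The same section lists clinic blood-pressure threshold counts on the same visit schedule.

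SAP 7.2.3 fixes the analysis set: "Analysis of exploratory endpoints will be performed on the PP population using the observed case data". The threshold endpoints get a descriptive summary. The section then says: "No sensitivity analysis is planned for the exploratory endpoints".

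SAP 5.4 defines the PP population. Besides at least 80% compliance and no major deviation that affected the ABPM readings, it requires:
- "Last daily dose of study drug administered on the same date that ABPM was initiated at Visit 4A";
- "Had at least 23.5 hours of ABPM data (i.e. blood pressure and heart rate data) at baseline and at Week 8/End of Study". A recording made when a subject stops early can serve as the final one, and three quarters of the readings must be present.

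SAP 7.1 lets the ITT population support efficacy analyses where appropriate, but ties that to no heart-rate table. The ITT analyses that are committed cover 24-hour SBP (SAP 7.2.1.1) and mean change in clinic SBP and DBP (SAP 7.2.2).

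**The concern.** All four PP conditions can act after randomisation, so membership may depend on tolerability and on what happened at the last visit. The clinic counts show this most plainly. A subject with a clinic heart rate above 100 bpm at Week 4 who later has no adequate final recording does not appear in the Week 4 count, although a clinic reading needs no ABPM device.

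Heart rate matters for this product. Protocol 4.1 names tachycardia as a possible reaction to phentermine and reports that heart-rate increases persisted at the top dose of the combination. Ambulatory monitoring is also the main planned record of the hours after dosing. Subjects are told to hold their dose on visit mornings, and Visit 4A vital signs precede ABPM hook-up and dosing, so clinic heart rate is largely a pre-dose measure. If ambulatory heart rate and the threshold counts exist only for PP subjects, a reader cannot check whether the between-arm picture depends on who complied and completed the final recording.

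**Working it through.** **Who is lost: baseline or final recording?** A 24-hour recording has 16 h × 3 + 8 h × 2 = 64 scheduled readings. 75% of 64 is 48, which reproduces the count in SAP 5.4. Sites must check the baseline recording against a stricter rule in Protocol 11.4: "at least 80% of the readings are valid, (2) there are at least 24 hours of data". 80% of 64 is 51.2, so 52 readings against 48, and 24 hours against 23.5. A failed recording is repeated. Protocol 10.2 instructs sites: "Contact EDC/RTSM to obtain randomization assignment for subject upon verifying successful ABPM". Protocol 9.4.3 adds: "Study drug will not be dispensed until the morning of Day 2 after the ABPM device is removed". The baseline criterion should therefore remove few subjects. The losses that matter come from the final recording, the dose date, compliance and major deviations.

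**What all-treated subjects do get**

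| Output | Population | Threshold counts? | Post-dose hours? |
|---|---|---|---|
| Clinic heart rate, values and change by visit (SAP 7.3.3; min/max per 7.1.1) | Safety | No | Largely pre-dose |
| ECG heart rate and clinically significant abnormalities (SAP 7.3.5) | Safety | No | Screening and Visit 4B only |
| TEAEs (SAP 7.3.1) | Safety | Only findings that meet Protocol 12.1.3 | Not a measurement |
| ABPM listing with heart rate (SAP 7.2.3) | Not stated | No, listing only | Yes, but no group summary |
| Clinic heart-rate thresholds (SAP 4.3, 7.2.3) | PP | Yes | Largely pre-dose |
| Ambulatory heart rate (SAP 4.3, 7.2.3) | PP | Yes | Yes |

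Two cells stay empty for all treated subjects: the clinic threshold counts and a group summary of ambulatory heart rate.

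**How many.** The documents give no PP exclusion rate. With 185 per arm, an assumed 5% (equal to the planned drop-out) is 185 × 0.05 = 9.25; 10% is 18.5; 20% is 37.

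**Possible size, illustration only.** Let e be the share excluded and d the excluded-minus-retained gap in heart-rate change (V = VI-0521, C = comparator). Within an arm, the all-treated mean is the retained mean plus e × d, so PP minus all-treated is −e × d. For the between-arm difference:

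bias = eC × dC − eV × dV

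If e and d are equal across arms, the bias is 0. Assume dC = 0, equal e in both arms, and dV from −3 bpm (excluded subjects off drug) to +6 bpm (poor tolerance):

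| e per arm | dV = −3 | dV = +6 |
|---|---|---|
| 5% | +0.15 bpm | −0.30 bpm |
| 10% | +0.30 bpm | −0.60 bpm |
| 20% | +0.60 bpm | −1.20 bpm |

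With the same gap in both arms but eV = 10% and eC = 5%: d = −3 gives −0.15 + 0.30 = +0.15 bpm, and d = +6 gives 0.30 − 0.60 = −0.30 bpm.

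For a threshold percentage, with dC = 0 and dV from −5 to +20 percentage points:
- e = 5%: +0.25 to −1.0 points, or 0.46 to 1.85 subjects per 185.
- e = 20%: +1.0 to −4.0 points, or 1.85 to 7.4 subjects per 185.

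Every e and d here is an assumption. The sign changes with dV.

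**The case against.** The strongest reply is that heart rate in all treated subjects is not unseen. The Safety Population outputs in the table above would show a shift in mean clinic or ECG heart rate, and the clinic maximum in each arm. Tachycardia with symptoms, needing treatment or judged significant would be an adverse event. This stands, and it narrows the gap to threshold counts and ambulatory heart rate.

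A reader might infer that the SAP treats heart rate worse than blood pressure, because SAP 7.2.2 gives clinic SBP and DBP an ITT analysis. The documents do not support that. The ITT analysis is of mean change; the clinic blood-pressure threshold counts sit on PP like the heart-rate counts, and clinic heart-rate change has its own Safety Population summary.

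A reader might also infer a breach, since Protocol 13.1 puts all analyses on ITT. The same section lets the SAP modify the plan and asks for an amendment only for major changes to the primary endpoint or its analysis.

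Nor are all early terminators lost. Withdrawn subjects undergo end-of-study procedures (Protocol 8.3), failed final recordings are repeated (Protocol 10.4), and a subject with an adequate early-termination recording who meets the other criteria stays in PP.

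The background is also milder than the word tachycardia suggests. Protocol 4.1 calls the increases with phentermine alone modest and expects minimal cardiovascular effects at therapeutic doses. Those modest increases were seen at 7.5 and 15 mg, however, and the comparator here is 30 mg.

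Finally, an on-drug set is a reasonable choice for post-dose heart rate. That supports keeping the PP tables; it does not support having only them. Setting dC = 0 in the illustration is also generous when the comparator is phentermine, itself active.

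**Conclusion.** The point holds and is minor. The SAP commits to no all-treated clinic threshold counts, for heart rate or blood pressure, and to no all-treated group summary of ambulatory heart rate. The clearest defect is that conditions met or failed around the final visit decide whether a Week 4 clinic reading is counted.

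The endpoints are exploratory, the threshold tables are descriptive, and all of them lie outside the testing hierarchy, so no formal claim depends on them. A reader might infer that the PP restriction conceals a heart-rate harm. The documents do not support that: they give no exclusion rate and no heart-rate spread, excluded subjects could run higher or lower, and the between-arm bias is zero if exclusion and its link to heart rate are equal across arms. On the assumed gaps with dC = 0, 5% exclusion per arm moves the mean difference by 0.15 to 0.30 bpm; 20%, for which the documents give no source, moves it by 0.60 to 1.20 bpm.

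**What to change.** In SAP 7.2.3 and 7.3:
- Produce the clinic heart-rate and clinic blood-pressure threshold tables on the Safety Population at each post-baseline visit, including Week 4.
- Repeat the ambulatory heart-rate mean-change tables and the tables of counts above 100 bpm for all treated subjects with a baseline and any post-baseline ABPM, including early termination. Show the number of valid readings.
- Keep the PP versions alongside, labelled as the on-drug view.

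No separate report of PP exclusions is needed. Discontinuation reasons (SAP 6.1), compliance (6.5), major deviations (6.7) and ABPM completeness (7.2.1.1) are already summarised. At most, one combined table by arm would help.

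The cost is SAP wording and a rerun of planned programs on a wider set, with no new data. The downside is that off-drug or short recordings may dilute the effect or add noise in the wider set. Subjects with no post-baseline recording remain missing from the ambulatory tables.
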